Modulation Effects of a Computer-based Multimodal Mind and Body Approach for Mild Cognitive Decline

NCT06814483

04/11/2024

Mild cognitive impairment (MCI) is believed to be the first cognitive expression of Alzheimer's disease (AD). Nevertheless, pharmacologic treatment for MCI is far from satisfactory, highlighting the urgent need for a cost-effective and easily implementable solution for MCI. Recently, mind and body approaches have demonstrated their potential for the prevention of cognitive decline and memory loss. Nevertheless, most of the studies / programs have focused on a single approach, and responses to each of these approaches are heterogeneous. The aim of this study is to perform a pilot feasibility study on computer-based multimodal mind and body approach (cbMMBA) for MCI, which integrate several promising mind and body approaches.

Specific Aim: Perform a feasibility study on the cbMMBA. individuals with MCI will be recruited and randomized to the cbMMBA group or a standard cognitive training group (Control condition – computer based cognitive fitness program (cbCFP). Primary outcomes will be feasibility-related assessments (recruitment, retention, fidelity, satisfaction and safety).

Detailed experimental procedure

Subject recruitment. Patients with MCI will be recruited.

Randomization. Patients who pass the screening will be randomized to the cbMMBA or cbCFP control group using a centrally generated, variable-sized block design.

Endpoints. Primary outcomes will be feasibility-related outcomes such as recruitment, retention, fidelity, satisfaction, and safety. Secondary outcomes will include cognitive assessments.

Blinding. Due to the nature of the intervention, patients cannot be blinded as to whether they receive cbMMBA or cbCFP control. All outcome assessors will be blinded to the treatment each patient receives.

Session 1 will be a baseline session that will include clinical outcome measures and other related assessments

Interventions All participants will receive cbMMBA or cbCFP three times per week for the first six weeks and two times per week for the remaining six weeks. All training will be remote over Zoom. Staff will also be available by phone to provide help if needed. Each session will last about one hour, with 1-2 breaks during the session. During the intervention, the pre-developed programs will be presented, and the instructor will be available to answer questions at the end of the session. Absent participants will receive a reminder phone call to attend subsequent sessions. Research staff will monitor home practice adherence through monthly phone calls and practice diaries during the follow-up.

Session 2-4 is Mid-term, final and follow-up assessments The mid-term and final assessments will be identical to the baseline assessment. A mid-term (6 week) assessment will allow us to better understand the projection of the intervention. Upon completion of the training programs at week 12, participants will be encouraged to continue with interventions at home and fill out weekly diary entries for an additional three months. At the end of this period, we will perform a follow-up assessment identical to the baseline assessment.

Modulation Effects of a Computer-based Multimodal Mind and Body Approach for Mild Cognitive Decline

NCT06814483

04/11/2024

Biostatistical analysis plan

The intention-to-treat (ITT) population included all randomized participants who received at least one session of the assigned intervention and was used for all feasibility, exploratory efficacy, and safety analyses. The per-protocol (PP) and safety populations were identical to the ITT set, as all participants initiated the intervention and were monitored for adverse events throughout the study.

Consistent with NIH recommendations for feasibility studies, we will report the following feasibility outcomes: 1) recruitment: proportion of participants that are enrolled from the total number of patients screened; 2) retention: proportion of subjects who complete all assessments from the total number of subjects who received one intervention session; 3) fidelity: the proportion of completed/planned intervention sessions (cbMMBA or cbCFP control); 4) satisfaction: proportion of participants having therapy satisfaction scores above the midpoint; and 5) safety: symptoms and adverse events reported by the participants.

For exploratory analysis of secondary cognitive and clinical outcomes, we will: explore the effects of the cbMMBA and cbCFP using mixed-model regression. The regression model will include subject as a random effect; fixed effects will include treatment group, treatment time point (baseline, 6 weeks, 12 weeks, and 24 weeks), and their interaction. Covariates such as age, gender, and ERS scores will also be included in the model to reduce subject heterogeneity.

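### Does a per-protocol set with no adherence criterion leave session attendance unmeasured?

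*SAP*

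**What the plan says.** The SAP (Biostatistical analysis plan, opening paragraph) defines the ITT set as "all randomized participants who received at least one session of the assigned intervention" and says that it "was used for all feasibility, exploratory efficacy, and safety analyses". It then adds: "The per-protocol (PP) and safety populations were identical to the ITT set, as all participants initiated the intervention". The sentence goes on to give adverse-event monitoring as a further reason.

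Two of the five feasibility outcomes in the next paragraph bear on the point:

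- Item 2: "retention: proportion of subjects who complete all assessments from the total number of subjects who received one intervention session".
- Item 3: "fidelity: the proportion of completed/planned intervention sessions (cbMMBA or cbCFP control".

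The protocol (Endpoints) makes both primary: "Primary outcomes will be feasibility-related outcomes such as recruitment, retention, fidelity, satisfaction, and safety". Under Interventions it schedules sessions "three times per week for the first six weeks and two times per week for the remaining six weeks" and foresees missed ones: "Absent participants will receive a reminder phone call to attend subsequent sessions". It sets no minimum attendance. Its only use of the word adherence concerns home practice after week 12, not the supervised sessions.

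**The concern.** A per-protocol set normally holds the participants who received the treatment broadly as planned. Here it is equated with ITT for two reasons that do not concern adherence. Starting treatment is the entry condition for ITT, and adverse-event monitoring is a condition for the safety set. A reader who sees that PP equals ITT could take it to mean that everyone adhered.

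The other outcomes do not obviously correct that impression. Retention counts people who finish the assessments, however few sessions they attended. Fidelity counts sessions, and the SAP does not say whether it will be pooled or worked out per participant. Recruitment, satisfaction and safety do not use attendance. So no stated outcome sorts participants by the number of sessions attended.

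Feasibility is the purpose of this pilot, so this could matter. A second-half schedule that nobody sustains and an early loss of a subgroup would call for different decisions about a larger trial, yet both could give the same fidelity figure.

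**Working it through.** **Inputs.** The session schedule comes from the protocol (Interventions). The set definitions and outcome definitions come from the SAP. Neither document gives a sample size, an expected fidelity or a session total, so there is no stated figure to reproduce. The participant numbers below are assumptions chosen for illustration.

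**1. Planned sessions.** Weeks 1–6: 3 × 6 = 18. Weeks 7–12: 2 × 6 = 12. Total 30 per participant.

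**2. What the PP label admits.** One session is 1/30 = 3.3%. Stopping at week 6 is 18/30 = 60%. On the stated reasons both are per-protocol, and both are retained if all assessments are completed. This part of the concern is right.

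**3. Which results use the PP set.** The SAP lists five feasibility outcomes and a mixed model for the secondary outcomes. It assigns feasibility, exploratory efficacy and safety analyses to the ITT set. Number of analyses run on the PP set: 0. Redefining or removing the set changes no planned estimate.

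**4. Can one fidelity figure hide two patterns?** Let a share f attend all 30 sessions and the rest attend one, with a mean of 18: 30f + 1(1 − f) = 18, so f = 17/29. Taking 29 people gives whole numbers.

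| | A: all stop at week 6 | B: 17 attend 30, 12 attend 1 |
|---|---|---|
| Sessions completed | 29 × 18 = 522 | 17 × 30 + 12 × 1 = 522 |
| Fidelity, of 29 × 30 = 870 | 60.0% | 60.0% |
| Weeks 1–6, of 29 × 18 = 522 | 522/522 = 100% | (17 × 18 + 12)/522 = 318/522 = 60.9% |
| Weeks 7–12, of 29 × 12 = 348 | 0/348 = 0% | (17 × 12)/348 = 204/348 = 58.6% |
| Attended all 30 | 0/29 = 0% | 17/29 = 58.6% |

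So a single session proportion does not fix the pattern. A milder assumed case shows the same. With 20 people and 80% fidelity (480 of 600 sessions), the number attending at least 24 sessions can be anywhere from 3 to 20. At the lower end 30k + 23(20 − k) ≥ 480 gives k ≥ 20/7, so k = 3. At the upper end 20 × 24 = 480.

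**5. Do the planned outcomes separate A from B anyway?**

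- *Retention.* Let j of the 12 one-session participants in B complete every assessment (baseline, 6, 12 and 24 weeks). Retention in B is then at most (17 + j)/29, from 17/29 = 58.6% when j = 0 to 29/29 = 100% when j = 12. In A it can reach 100%. The two patterns share the same retention ceiling only if all 12 people who left after one session return for every later assessment.
- *Fidelity per participant.* All participants have 30 planned sessions, so the pooled proportion equals the mean of the individual proportions. The spread differs. In A every value is 18, so the SD is 0. In B the variance is [17 × (30 − 18)² + 12 × (1 − 18)²]/29 = (2448 + 3468)/29 = 204, so the SD is √204 ≈ 14.3 sessions. Any routine measure of spread tells the two apart.

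**6. Does the PP wording cause the gap?** No. Fidelity would be just as aggregated if the PP set were removed, since removal adds no count by participant. The same sentence also defines the safety set and mentions adverse-event monitoring, so simply striking it out would lose wording that the plan needs.

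**The case for a change.** The strongest case for a change is that it costs almost nothing and would sharpen a primary outcome. Completed sessions must be recorded for fidelity, and reminder calls require knowing who was absent. Median and range of sessions per participant, attendance in each half, and the number with no session after week 6 would therefore need no new data and no cut-off. The SAP does not promise a measure of spread, so the separation shown by the SD depends on the analysts choosing to report one. The retention argument also depends on behaviour: if people who stop attending still return for assessments, retention will not reveal it.

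Much of this stands. The PP label is poorly justified, a bare fidelity percentage is less informative than a distribution, and a halves breakdown suits a schedule that changes at week 6. What does not stand is the step from there to a defect in the plan. Retention is clearly defined and is not faulty for leaving sessions to fidelity. Fidelity measures attendance directly, and its wording names both programmes. How finely to tabulate it is a reporting choice that the analysts can make from records they will hold, with no amendment to the plan.

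**Conclusion.** The observation is correct but has no consequence for the planned results. The PP set has no adherence criterion, and its effective threshold is 1 of 30 sessions. No analysis uses it, so the effect on every planned estimate is zero. Session attendance is not left out: it is a primary outcome through fidelity. The case in which fidelity and retention both fail to distinguish two attendance patterns uses an invented group of 29 at 60% fidelity. It also needs all 12 one-session participants to complete every assessment; if none does, retention in that pattern is at most 58.6%, against up to 100% in the other.

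The remaining gap is descriptive detail that a sensible analyst supplies when writing up fidelity. This conclusion assumes that attendance is recorded for each participant, as the reminder calls imply, and that no per-protocol analysis is added later. If one were added, the set would first need an adherence criterion chosen by the sponsor and fixed before outcome data are reviewed. As the plan stands, no change is needed.

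### Does the satisfaction outcome need a stated questionnaire, rating visit and denominator before its result can be read?

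*SAP*

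**What the plan says.** The Protocol, under Endpoints, makes satisfaction primary: "Primary outcomes will be feasibility-related outcomes such as recruitment, retention, fidelity, satisfaction, and safety". The SAP's list of feasibility outcomes gives its only definition: "satisfaction: proportion of participants having therapy satisfaction scores above the midpoint".

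The SAP's population paragraph defines the ITT set as everyone randomized who had one or more sessions, and says that this set "was used for all feasibility, exploratory efficacy, and safety analyses". It adds: "The per-protocol (PP) and safety populations were identical to the ITT set". No named population is therefore restricted to people with a satisfaction score.

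Beside satisfaction the SAP lists "retention: proportion of subjects who complete all assessments from the total number of subjects who received one intervention session". Of the later visits, the Protocol says: "The mid-term and final assessments will be identical to the baseline assessment". The follow-up visit is described in the same way. Satisfaction is not placed at any visit.

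**The concern.** A primary outcome should be computable from its definition, and this one leaves four things open: the instrument (and so the value of the midpoint), the time of rating, the denominator, and the handling of missing scores. The general ITT sentence seems to settle the denominator, and it does so awkwardly. Over the whole ITT set, the figure is the share scored multiplied by the share of those scored who are above the midpoint. Someone who left before rating then counts as dissatisfied.

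If that were the rule, a low figure could mean unhappy participants or missing forms, and the outcome would partly duplicate retention. Two arms with equal satisfaction could look different because of dropout alone, or a real difference could be hidden. Dividing by respondents avoids this but may favor people who stayed. The two choices can give visibly different numbers for a primary outcome, so the missing rule looks like a defect.

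**Working it through.** **No figure to reproduce.** The documents give no sample size, expected satisfaction, dropout rate or feasibility target. Every input below is assumed.

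**Formulas.** Let *p* be the share above the midpoint among those scored, and *u* the share of the ITT set with no score.

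- Respondent figure: *p*
- All-ITT figure, unscored counted as not above: *p*(1 − *u*)
- Gap between the two: *p* × *u*
- Highest possible full-set value, all unscored counted as above: *p*(1 − *u*) + *u*

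With *p* = 0.80:

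| *u* | Respondents | All ITT | Gap | Highest possible |
|---|---|---|---|---|
| 0% | 80% | 80% | 0 | 80% |
| 5% | 80% | 76% | 4 points | 81% |
| 10% | 80% | 72% | 8 points | 82% |
| 20% | 80% | 64% | 16 points | 84% |
| 30% | 80% | 56% | 24 points | 86% |

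The gap stays under 5 points only if *u* is below 0.05/0.80 = 6.25%. It is zero if everyone is scored.

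**Between arms.** With 80% satisfied in both arms but 90% and 70% scored, the all-ITT figures are 0.80 × 0.90 = 72% and 0.80 × 0.70 = 56%. With 90% satisfied and 80% scored against 80% satisfied and 90% scored, both are 72%.

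**Dependence on rating time.** Suppose 20% drop out and a fraction *f* of them rated before leaving. The all-ITT figure is 0.80 × (1 − 0.20 × (1 − *f*)): 64% at *f* = 0, 72% at *f* = 0.5 and 80% at *f* = 1. Early or repeated rating shrinks the effect or removes it.

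**Does the SAP impose the all-ITT reading?** Compare the denominators of its feasibility items:

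| Item | Denominator in the SAP |
|---|---|
| Recruitment | patients screened |
| Retention | people who received one session |
| Fidelity | planned sessions |
| Satisfaction | none stated |
| Safety | none stated |

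Recruitment cannot be computed over the ITT set, because people screened but never randomized lie outside it. Fidelity counts sessions, not people. The general ITT sentence therefore says whose data are used and does not set the divisor of each item. The satisfaction clause fits all ITT participants or only those with a score, and no sentence counts an unscored participant as dissatisfied.

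**Do the documents predict missing scores?** Having a retention outcome does not predict loss. The sentence "Absent participants will receive a reminder phone call to attend subsequent sessions" concerns missed training sessions, not unreturned questionnaires. Retention also requires every assessment, including follow-up, so someone who misses only that visit fails retention but may already have rated satisfaction.

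**What normal reporting supplies.** Let *N* be the ITT number, *n* the number scored and *k* the number above the midpoint. The respondent figure is *k*/*n*, the all-ITT figure is *k*/*N*, and *u* = 1 − *n*/*N*. Three counts give every version above.

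**The case for a change.** The strongest case for a change is that these proportions are the main product of a feasibility pilot. Two defensible readings that can differ by 16 points at 20% unscored (with *p* = 0.80) are a reason to fix one in advance. Recruitment, retention and fidelity each state a denominator and satisfaction does not, so the ITT sentence is the only one it could inherit. The visit schedule does not help: therapy satisfaction cannot be rated before therapy, yet the later assessments are said to repeat baseline. Dividing by respondents is not neutral either. With 20% unscored, of whom 40% would have been above the midpoint, the full-set value is 0.80 × 0.80 + 0.20 × 0.40 = 72%, which neither the 80% nor the 64% figure reports.

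Much of this stands. The four omissions are real, and the identity *p*(1 − *u*) is correct. What does not stand is the step from an unstated denominator to a stated rule that misleads. The schedule sentence is best read as describing the outcome battery: adverse events and session counts are not placed at a visit either, yet both are clearly to be collected. The lack of a named questionnaire is also not special to satisfaction, since the Protocol names no cognitive instrument. It reflects the brevity of a short pilot plan.

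**Conclusion.** No change to the plan follows. The SAP leaves out detail that an analyst must supply to produce the result at all: which questionnaire, when it was given, how many were scored and how many were above the midpoint. Once those counts are shown, a reader can form either proportion and see how much is missing.

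The possible discrepancy is *p* × *u*: nil with complete scores, and 8 to 24 points for 10% to 30% unscored at an assumed 80%. Those sizes rest wholly on assumed inputs, and on people who leave having given no rating, which the documents neither state nor exclude.

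The consequence is also limited. The plan sets no satisfaction target, go/no-go rule or test. Its only stated group model is for the secondary outcomes, and the SAP does not say whether satisfaction is reported by arm, so the between-arm distortion concerns a comparison that is not planned. Retention is to be reported too and gives a rough, though not exact, view of attrition. Part of the SAP's population text is in the past tense ("as all participants initiated the intervention and were monitored for adverse events throughout the study"), so the remaining task may simply be to report what was done. That wording does not show that satisfaction scores were complete, and this conclusion does not rely on it.

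### Cheap improvement, not an error (exploratory outcomes only): if Session 1 precedes disclosure of allocation, a common baseline mean would give modestly more precise group differences

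*SAP*

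**What the plan says.** The Biostatistical analysis plan in the SAP gives the model for the exploratory secondary outcomes in three statements:

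- Correlation: "The regression model will include subject as a random effect".
- Fixed effects: "fixed effects will include treatment group, treatment time point (baseline, 6 weeks, 12 weeks, and 24 weeks), and their interaction".
- Covariates: "Covariates such as age, gender, and ERS scores will also be included in the model to reduce subject heterogeneity".

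The SAP names neither the outcome's own baseline score as a covariate nor a common baseline mean for the arms. It does not say which contrast will be reported as the group effect.

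The Protocol supplies the design facts:

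- Randomization: "Patients who pass the screening will be randomized to the cbMMBA or cbCFP control group".
- Blinding: "patients cannot be blinded as to whether they receive cbMMBA or cbCFP control". Outcome assessors are blinded.
- Baseline: "Session 1 will be a baseline session that will include clinical outcome measures and other related assessments".
- Later visits: "The mid-term and final assessments will be identical to the baseline assessment". The follow-up assessment is described in the same way.

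On the analysis set, the SAP reports that "all participants initiated the intervention and were monitored for adverse events throughout the study".

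**The concern.** A group term together with a group-by-time interaction over four visits lets the arms have different true means at baseline. When baseline is measured before allocation is known, randomization makes those means equal in expectation, and any observed difference is chance. Estimating it freely discards information that would sharpen the comparison at later visits.

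The ingredients for using that information are in place. The same assessment is made at every visit, so the baseline score is already collected. The SAP says every participant started the intervention, so the one-session condition in its ITT definition should not have removed anyone and disturbed the balance.

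At stake is the width of the intervals around the pilot's only comparative estimates of cognitive effect. No primary feasibility outcome depends on this model.

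**Working it through.** **Inputs.** The visits (baseline, 6, 12 and 24 weeks) and the random subject effect come from the SAP. A random subject effect implies one correlation, rho, between any two visits. The documents give no rho, sample size or covariate strength. Assumed here: rho 0.5 to 0.9, complete data, equal arms of n, and known variances for the closed forms. The plan states no figure to reproduce.

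**Closed forms.** In units of 2·sigma²/n, the variance of the group contrast at a post-baseline visit is:

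- planned model, difference in change from baseline (interaction): 2(1 − rho);
- planned model, difference at that visit (group plus interaction): 1;
- common-baseline model: 1 − rho².

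The common-baseline variance is therefore (1 + rho)/2 of the first and 1 − rho² of the second. Against the better planned contrast the ratio is max((1 + rho)/2, 1 − rho²). The two terms meet where 1/2 = 1 − rho, at rho = 0.5. The minimum is 0.75, and √0.75 = 0.866, so the standard error falls by at most about 13%.

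**Without covariates**

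| rho | change | visit | common baseline | ratio to better | SE falls by |
|---|---|---|---|---|---|
| 0.5 | 1.00 | 1 | 0.75 | 0.75 | 13% |
| 0.7 | 0.60 | 1 | 0.51 | 0.85 | 8% |
| 0.8 | 0.40 | 1 | 0.36 | 0.90 | 5% |
| 0.9 | 0.20 | 1 | 0.19 | 0.95 | 3% |

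Example with an assumed 20 per arm, SD 1 and rho 0.7: the SE is √(0.1 × 0.60) = 0.245 for the change contrast and √(0.1 × 0.51) = 0.226 with a common baseline.

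**With covariates.** Suppose age, gender and ERS explain 30% of between-subject variance. The residual variance is 1 − 0.3·rho, and the residual correlation is rho' = 0.7·rho/(1 − 0.3·rho).

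| rho | rho' | (1 + rho')/2 | 1 − rho'² | ratio to better | SE falls by |
|---|---|---|---|---|---|
| 0.5 | 0.412 | 0.706 | 0.830 | 0.83 | 9% |
| 0.7 | 0.620 | 0.810 | 0.615 | 0.81 | 10% |
| 0.8 | 0.737 | 0.868 | 0.457 | 0.87 | 7% |
| 0.9 | 0.863 | 0.932 | 0.255 | 0.93 | 3% |

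**If correlation decays over time.** Take AR(1) with the same correlation r for each step between visits. The random-intercept model then works with the average of the six pairwise correlations, w = (3r + 2r² + r³)/6. At week 24 the common-baseline estimate has true variance 1 + w² − 2w·r³, and the change contrast has 2(1 − r³).

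- r = 0.7: w = 0.571. Variance 0.934 against 1 (visit) and 1.314 (change), giving ratios 0.93 and 0.71.
- r = 0.5: w = 0.354. Variance 1.037 against 1 and 1.75, giving ratios 1.04 and 0.59.

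The gain over the change contrast remains. The gain over the single-visit contrast nearly disappears at 0.7 and becomes a small loss at 0.5.

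**Small samples.** Simulation with three covariates and complete data gives these variances relative to the change contrast, at rho 0.5, 0.7 and 0.9:

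| Form | total N 20 | total N 40 |
|---|---|---|
| Common baseline (REML, 12,000 replicates) | 0.76, 0.85, 0.95 | 0.73, 0.83, 0.94 |
| Baseline score as covariate (40,000 replicates) | 0.84, 0.98, 1.12 | 0.76, 0.88, 1.01 |

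The Monte Carlo standard error is at most 0.007. The second form can lose its gain at high rho.

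**Coding check.** Group, time and interaction use 4 + 1 + 3 = 8 parameters. Dropping only the group main effect from a factor-coded model still leaves 4 + 4 = 8, which is the same model. The true constraint has 4 + 3 = 7.

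**The case against.** The strongest reply is that this is a choice between two valid models in an exploratory analysis of a feasibility pilot, with no test, power claim or decision rule attached. That stands, and it is why the point is offered as an improvement.

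The second reply is that the constraint rests on a fact the documents do not give. The Protocol describes randomization before Session 1, and patients are unblinded. If they knew their arm before baseline, a real baseline difference could exist and the constraint could bias the comparison. This also stands, so the timing question comes first. A reader might infer from the order of the text that baseline follows disclosure, but order of description is not a statement of timing.

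A reader might also infer a much larger gain from the single-visit comparison, where the covariate-adjusted ratios reach 0.46 and 0.26 at rho 0.8 and 0.9. The documents do not support that as the headline. The SAP does not name its reported contrast, and its interaction term already gives the change contrast, which is the more precise of the two at those correlations. The large ratios also fail under decaying correlation. In that case the model-based variance is too small as well (0.675 against a true 0.934 at week 24, r = 0.7), but the planned change contrast shares this fault: 2(1 − 0.571) = 0.86 against 1.31.

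**Conclusion.** The point holds as a modest, conditional improvement to the exploratory analysis. A reader might take the missing baseline covariate as a sign of bias. It is not: in a randomized comparison the planned model is valid, and it only leaves some precision unused.

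Under a common correlation and complete data, the standard error falls by at most about 13% against the better planned contrast, and by about 3% to 10% over the assumed range with covariates. Some dropout changes this little: with 10% lost after week 6 and 10% after week 12, the week-24 ratio to the change contrast at rho 0.7, without covariates, is 0.87 instead of 0.85. The exact gain cannot be fixed, because the documents give neither rho nor sample size. Any gain requires that Session 1 be completed before patients learn their allocation, which the documents leave open.

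**What to change.** 1. Confirm, and state in the SAP, whether Session 1 is completed before patients learn their allocation.
2. If it is, constrain the arms to a common baseline mean. Remove both the group main effect and the baseline-by-group term, so that group effects exist only at weeks 6, 12 and 24. Keep age, gender and ERS, measured before disclosure, as covariates. Report the adjusted group difference at each visit. Each arm's course from baseline can still be described.
3. If it is not, keep the planned model and name the group-by-time difference in change as the reported contrast.
4. Do not use the baseline score as a covariate in place of the constraint if the sample is small, because that form's gain can vanish.

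The cost is a timing check, a few sentences of SAP text and recoded fixed effects, with no new data. The SAP describes its populations in the past tense. If outcome data have already been seen, the adjusted analysis should be labelled post hoc and shown beside the planned one.
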